7.1.1.4. Sensitivity Analysis

Sensitivity analyses will be performed for the primary efficacy endpoint to assess the robustness of the primary efficacy analysis results with respect to different methods of handling missing values. Detailed methodology is provided in [Appendix 6: Premature Withdrawals & Handling of Missing Data](#).

7.1.2. Planned Efficacy Statistical Analyses

Primary Statistical Analyses
Endpoint(s)

 Change from baseline in HbA_{1c} at Week 26
Model Specification

 Multiple imputation: Use PROC MI by specifying BY treatment group, using MCMC statement with the option chain = multiple and including baseline and all post-baseline scheduled visits up to Week 26. Then the imputed values at Week 26 for the liquid drug product arm will be replaced with the originally imputed values plus 0.4. MMRM model: Change from Baseline in HbA_{1c} = Baseline HbA_{1c} + Treatment + Region + Age Category + Weight Category + Background Antidiabetic Therapy + Visit Week + Treatment-by-Visit Interaction + Baseline HbA_{1c}-by-Visit Interaction. This model will be including all HbA_{1c} values collected at scheduled visits from Week 4 up to Week 26 and will be performed for each imputation. Combining analysis results: Use PROC MIANALYZE by applying the MODELEFFECTS and STDERR statement. The treatment differences, confidence intervals and p-values will be estimated by combining the multiple sets of MMRM results..
Model Checking & Diagnostics

 Refer to Appendix 11: Model Checking and Diagnostics for Statistical Analyses.
Model Results Presentation

 The treatment difference at Week 26 and its 1-sided 97.5% confidence interval (or equivalently 2-sided 95% confidence interval) estimated from the combined MMRM results from multiple imputation. Descriptive statistics for the observed HbA_{1c} and change from Baseline HbA_{1c} Refer to Appendix 14 List of Data Displays
Supportive Statistical Analysis

 The primary endpoint will also be analyzed using the MMRM model above including all HbA_{1c} values collected at scheduled visits from Week 4 up to Week 26. This would include values after post-hyperglycemia rescue and discontinuation from investigational product. No explicit data imputation will be performed. The primary endpoint will also be analyzed using the MMRM model above excluding post-hyperglycemia rescue data and post discontinuation from study treatment data. No data imputation will be performed. The primary endpoint will also be analyzed using MMRM model above in the Per-Protocol Population. No data imputation will be performed.
Model Specification

 Same MMRM model as for the primary analysis
By-Subgroup Statistical Analysis

 The subgroup analyses will be performed using the same multiple imputation/MMRM model approach except in the MMRM step a treatment by subgroup interaction term is added to the model. The subgroups include baseline HbA_{1c} category, region, age category (<65 or ≥65 years), weight category (<90 or ≥90 kg), background antidiabetic therapy (diet and exercise or stable dose of metformin), gender, race, ethnicity and duration of diabetes category. Refer to Appendix 9: Examination of Covariates, Subgroups & Other Strata.

Model Specification

• Change from Baseline in HbA_{1c} = Baseline HbA_{1c} + Treatment + Region + Age Category + Weight Category + Background Antidiabetic Therapy + Visit Week + Treatment-by-Visit + Baseline HbA_{1c}-by-Visit Interaction + Subgroup (if not already in the model) + Subgroup-by-Treatment+ Subgroup-by-Visit + Subgroup-by-Treatment-by-Visit.• Refer to Appendix 11: Model Checking and Diagnostics for Statistical Analyses for SAS code
Sensitivity Statistical Analysis

• Refer to Appendix 6 Section 11.6.3.4: Sensitivity Analysis Under Missing Not At Random (MNAR)

8. SECONDARY STATISTICAL ANALYSES

8.1. Efficacy Analyses

8.1.1. Overview of Planned Efficacy Analyses

The secondary efficacy analyses will be based on the ITT population.

Table 4 provides an overview of the planned efficacy analyses, with further details of data displays being presented in Appendix 14: List of Data Displays.

Table 4 Overview of Planned Efficacy Analyses

Endpoint / Display Type	Stats Analysis			Summary		Individual	
	T	F	L	T	F	F	L
Change from baseline in FPG at Week 26	Y	Y		Y	Y		Y
Change from baseline in HbA1c over time	Y	Y		Y	Y		Y
Change from baseline in FPG over time	Y	Y		Y	Y		Y

NOTES :

- T = Table, F = Figure, L = Listing, Y = Yes display generated.
- Stats Analysis = Represents TFL related to any formal statistical analyses (i.e. modelling) conducted.
- Summary = Represents TFL related to any summaries (i.e. descriptive statistics) of the observed raw data.
- Individual = Represents FL related to any displays of individual subject observed raw data.

8.1.1.1. FPG Change from Baseline at Week 26 and over Time

FPG change from Baseline by visit will be analyzed using the similar MMRM model as described in Section 7.1.1.1 with FPG replacing HbA1c in the model without imputation. The observed FPG and change from Baseline FPG will be summarized descriptively and presented graphically. The least squares means (and standard errors) of change from Baseline FPG will be plotted by treatment group. The analyses will be performed on ITT population and all data will be listed.

8.1.1.2. HbA_{1c} Change from Baseline over Time

HbA_{1c} change from baseline by visit will be analyzed using the same MMRM model as described in Section 7.1.1.1 without imputation in the ITT population. The observed HbA_{1c} and change from baseline HbA_{1c} will be summarized descriptively and presented graphically. The least squares means (and standard errors) of change from Baseline HbA_{1c} will be plotted by treatment group.

8.2. Safety and Tolerability Analyses

8.2.1. Overview of Planned Analyses

The safety analyses will be based on the safety population.

Safety and exposure for subjects continuing in extension study 204682 will be summarized too.

[Table 5](#) provides an overview of the planned analyses, with further details of data displays being presented in [Appendix 14](#): List of Data Displays.

Table 5 Overview of Planned Safety Analyses

Endpoints	Observed				Change from Baseline			
	Summary		Individual		Summary		Individual	
	T	F	F	L	T	F	F	L
Injection Site Reaction	Y			Y				
Immunogenicity	Y			Y				
Adverse Events								
All AEs	Y			Y				
Pre-therapy, On-therapy, and Post-therapy AEs	Y			Y				
Relationship of AEs to Study Drug	Y			Y				
AEs by Maximum Intensity	Y			Y				
Most Common AEs	Y			Y				
Serious AEs	Y			Y				
AEs and SAEs Leading to Treatment Discontinuation	Y			Y				
Fatal AEs and non-fatal SAEs	Y			Y				
AEs of special interest	Y			Y				
Incidence of hypoglycemic events (in total and by each category as defined by the American Diabetes Association criteria)	Y							
Clinical Laboratory	Y	Y		Y	Y	Y		Y
Vital Signs	Y	Y		Y	Y	Y		Y
Electrocardiogram (ECG)	Y	Y		Y	Y			Y

NOTES :

- T = Table, F = Figure, L = Listing, Y = Yes display generated.
- Stats Analysis = Represents TFL related to any formal statistical analyses (i.e. modelling) conducted.
- Summary = Represents TFL related to any summaries (i.e. descriptive statistics) of the observed raw data.
- Individual = Represents FL related to any displays of individual subject observed raw data.

Following review of the data, additional analyses maybe conducted to further support the evaluation and interpretation of the data.

8.2.2. Injection Site Reactions

Injection site reactions are reported by the investigators on the eCRF. The number and percentage of subjects with injection site reactions and 95% confidence intervals of the proportions will be presented by treatment group. In addition, the time to first occurrence of an injection site reaction will be analyzed and presented in a manner identical to that described for the first occurrence of a GI event in Section 8.2.7.5.

The number and percentage of subjects reporting injection site reactions at each study week will be presented by treatment group. Each week will include those subjects with the onset of an injection site reaction during that particular week as well as those subjects with injection site reactions from previous weeks that have not resolved. The incidence of injection site reactions will be plotted over time. Various characteristics of injection site reactions at the event level and subject level will be summarized.

A by-subject listing of injection site reactions will also be produced.

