2.1. Study Rationale

Currently, lyophilized albiglutide and the diluent are provided in a DCC, single-dose pen injector, requiring reconstitution prior to use. A liquid formulation of albiglutide will enable the commercialization of a liquid product in a single dose, ready-to-use prefilled syringe in an auto-injector. To support the development of the liquid auto-injector product, Study 201287, a healthy volunteer bioequivalence study will be conducted as the first component of the comparability assessment and the proposed study, Study 200952, will be conducted as the final component of the overall comparability assessment.

Extensive release and characterization testing has been utilized in studies to establish the comparability between samples of the liquid product and commercial lyophilized product. These studies were performed to evaluate the relevant differences in the quality attributes of the liquid and lyophilized products. However, non clinical studies are not suitable for predicting clinically relevant comparability of immunogenicity potential.

The albiglutide lyophilized products has been evaluated in an international program of studies involving approximately 9000 subject-years of overall exposure to date (including over 4000 subject-years of exposure to albiglutide) and has been found to have a favorable benefit:risk profile, including a low immunogenicity profile. In the clinical program with the lyophilized product, a low incidence (4.4%) of ADA was detected. Antibodies were non-neutralizing and mostly low titer and transient in nature. None of the antibodies impacted the pharmacokinetic (PK), PD or efficacy of the drug. There was a higher frequency of ISRs in antibody positive subjects, however most subjects with an ISR (including those ISRs classified as serious) were antibody negative. There was no apparent relationship between antibody positive status and other AEs that could be attributed to albiglutide.

This repeat-dose study in T2DM patients will determine if there are any clinically relevant differences between liquid drug product stored under recommended storage conditions to lyophilized drug product with respect to efficacy, safety, tolerability and PD response. Specifically, the immunogenicity potential (e.g., incidences of ADA) and ISRs will be evaluated as part of the overall safety assessment in this study.

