9.4.2. Secondary Analyses

The evaluation of the safety and tolerability as assessed by immunogenicity and ISRs of albiglutide liquid drug product and the lyophilized drug product will be provided by reporting the event rates, and the associated 95% CI.

The overall general safety and tolerability of albiglutide liquid drug product versus lyophilized drug product will be evaluated in tabular and/or graphical format and summarized descriptively.

AEs and SAEs, physical examinations, clinical laboratory evaluations, vital sign measurements, and 12-lead electrocardiogram will be summarized by treatment group. For continuous variables, these summaries will include sample size, mean, median, standard deviation (and/or standard error), minimum, and maximum. For categorical variables, the summaries will include frequencies and corresponding percentages. The exposure-adjusted incidence rate will also be calculated as the number of events in a given period divided by the total person time on treatment of subjects at risk within the same period. The exposure-adjusted incidence rate will be expressed as an annualized rate expected. No inferential testing will be performed on the safety variables. Hypoglycemic events will be analyzed separately from other AEs. All hypoglycemic events will be classified as severe, documented symptomatic, asymptomatic, probable symptomatic, and pseudohypoglycemia, as defined in Section 7.4.9.

AEs will be coded using MedDRA. AEs will be summarized in various subsets, including on therapy AEs, related AEs, AEs leading to treatment discontinuation or withdrawal from study, SAEs, fatal AEs, etc. AEs will also be summarized by maximum intensity (mild, moderate, and severe).

Anti-albiglutide antibody results will be summarized by treatment group. In addition, the number and percentage of subjects with positive results along with the antibody titer values will be provided by visit.

The secondary endpoint FPG change from baseline at Week 26 will be analyzed using MMRM without imputation.

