3.61.	Safety		Overview of On-therapy Adverse Events of Special Interest		

CONFIDENTIAL

200952

Safety : Tables					
No.	Population	IDSL / TST ID / Example Shell	Title	Programming Notes	Deliverable [Priority]
3.71.	Safety		On-therapy Hypoglycemic Events by SAE Status, Relationship to Study Medication, and Withdrawal Status		
3.72.	Safety		On-therapy Hypoglycemic Events by Treatment, Symptom, Severity, Intervention and Action Taken		
3.73.	Safety		On-therapy Hypoglycemic Events by Blood Glucose Level		
3.80.	Safety		On-therapy Hypoglycemic Events over Time by Onset Week		
3.91.	Safety		On-therapy and Post-therapy Cardiovascular Adverse Events		
3.101.	Safety		On-therapy and Post-therapy Thyroid Adverse Events Reported by the Investigator		
3.102.	Safety		On-therapy and Post-therapy Thyroid Adverse Events Identified by a Customized MedDRA Query		
3.111.	Safety		Summary of Gastrointestinal Adverse Events		
3.112.	Safety		On-therapy Gastrointestinal Adverse Events		
3.113.	Safety		On-therapy Serious Gastrointestinal Adverse Events		
3.114.	Safety		On-therapy Treatment-related Gastrointestinal Adverse Events		
3.115.	Safety		On-therapy Gastrointestinal Adverse Events Leading to Permanent Discontinuation of Study Treatment before Scheduled End of Treatment Period		
3.116.	Safety		On-therapy Gastrointestinal Adverse Events over Time		
3.117.	Safety		On-therapy Gastrointestinal Adverse Events by Onset Week		
3.118.	Safety		Kaplan-Meier Analysis of Time to First Occurrence of a Gastrointestinal Adverse Event		
3.119.	Safety		On-therapy Nausea over Time		
3.120.	Safety		On-therapy Diarrhea over Time		

Safety : Tables					
No.	Population	IDSL / TST ID / Example Shell	Title	Programming Notes	Deliverable [Priority]
3.121.	Safety		On-therapy Vomiting over Time		
3.122.	Safety		On-therapy Nausea or Vomiting over Time		
3.131.	Safety		On-therapy and Post-therapy System Allergic Reactions Identified by the Investigator		
3.132.	Safety		On-therapy and Post-therapy System Allergic Reactions Identified by a Customized MedDRA Query		
3.133.	Safety		Kaplan-Meier Analysis of Time to First Occurrence of a Systemic Allergic Reaction Reported by the Investigator		
3.134.	Safety		Kaplan-Meier Analysis of Time to First Occurrence of a Systemic Allergic Reaction Identified by a Customized MedDRA Query		
3.141.	Safety		On-therapy and Post-therapy Injection Site Reactions		
3.142.	Safety		Kaplan-Meier Analysis of Time to First Occurrence of an Injection Site Reaction		

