3.143.	Safety		On-therapy Injection Site Reaction over Time		
3.144.	Safety		Summary Characteristics of On-therapy Injection Site Reactions		
3.151.	Safety		On-therapy and Post-therapy Liver Events Identified by a Customized MedDRA Query		
3.161.	Safety		On-therapy and Post-therapy Pancreatitis and Pancreatic Cancer		
3.162.	Safety		On-therapy and Post-therapy Adjudicated Pancreatitis Events		
3.171.	Safety		On-therapy and Post-therapy Atrial Fibrillation and Atrial Flutter Adverse Events		
3.181.	Safety		On-therapy and Post-therapy Pneumonia Adverse Events Reported by the Investigator		

Safety : Tables					
No.	Population	IDSL / TST ID / Example Shell	Title	Programming Notes	Deliverable [Priority]
3.182.	Safety		On-therapy and Post-therapy Pneumonia Adverse Events Identified by a Customized MedDRA Query		
3.191.	Safety		On-therapy and Post-therapy Diabetic Retinopathy Adverse Events		
3.201.	Safety		On-therapy and Post-therapy Appendicitis Adverse Events		
3.211.	Safety		On-therapy and Post-therapy Malignant Neoplasm Adverse Events Identified by a Customized MedDRA Query		
Lab Assessments					
3.221.	Safety		Change from Baseline in Hematology by Visit		
3.222.	Safety		Change from Baseline in Chemistry by Visit		
3.223.	Safety		Hematology Values of Clinical Concern by Visit		
3.224.	Safety		Chemistry Values of Clinical Concern by Visit		
3.225.	Safety		Liver Function Tests of Clinical Concern by Visit		
3.226.	Safety		Shift in Hematology by Visit		
3.227.	Safety		Shift in Chemistry by Visit		
3.228.	Safety		Urinalysis by Visit		
Vital Signs					
3.231.	Safety		Change from Baseline in Vital Signs by Visit		
3.232.	Safety		Vital Signs of Clinical Concern by Visit		
3.233.	Safety		Shift in Vital Signs of Clinical Concern by Visit		
[ECG]					
3.341.	Safety		Change from Baseline in ECG Values by Visit		
3.342.	Safety		ECG Values of Clinical Concern by Visit		

Safety : Tables					
No.	Population	IDSL / TST ID / Example Shell	Title	Programming Notes	Deliverable [Priority]
3.343.	Safety		Overall ECG Interpretations by Visit		
3.344.	Safety		Shift in ECG Values of Clinical Concern from Baseline to Week 26		
3.345.	Safety		ECG QTcF and QTcB Results of Notable Abnormalities at any time post-baseli		
Immunogenicity					
3.351.	Safety		Positive Immunogenicity Results for Anti-Albiglutide Antibody Positive Subjects by Visit		
3.352.	Safety		Positive Immunogenicity Results for Anti-Albiglutide Antibody Positive Subjects by Therapy Phase		

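### Injection site reactions are specified only by arm, but every subject gets both injectors, so reactions due to the liquid's pH, volume or device largely cancel between arms

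*SAP*

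**What the plan says.** SAP 8.2.2 sets out the ISR analysis: "The number and percentage of subjects with injection site reactions and 95% confidence intervals of the proportions will be presented by treatment group". The weekly summary is also by treatment group. Time to first ISR follows the method for gastrointestinal events in SAP 8.2.7.5, which reports Kaplan-Meier results for each treatment group. One further sentence is open-ended: "Various characteristics of injection site reactions at the event level and subject level will be summarized".

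The ISR tables in SAP 11.14.5 are 3.141 (on-therapy and post-therapy ISRs), 3.142 ("Kaplan-Meier Analysis of Time to First Occurrence of an Injection Site Reaction"), 3.143 ("On-therapy Injection Site Reaction over Time") and 3.144 ("Summary Characteristics of On-therapy Injection Site Reactions"). Figure 3.21 and Listing 25 complete the set. No title refers to the injector.

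Protocol 4.2 gives each arm one active and one placebo injector of opposite types. Protocol 6.1 has site staff give them weekly and describes the placebo liquid as having the active liquid's pH (5.9), volumes (0.6 mL and 1.0 mL), needle and auto-injector.

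Protocol 2.1 says that the study "will determine if there are any clinically relevant differences between liquid drug product stored under recommended storage conditions to lyophilized drug product", with ISRs named for specific evaluation. Protocol 9.4.2 adds: "No inferential testing will be performed on the safety variables".

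**The concern.** Protocol Table 2 (Section 4.6.1) gives the liquid's lower pH and its larger volume at the 50 mg dose as examples of formulation differences that could change the ISR profile. It also says that nobody has experience of placebo given by the liquid auto-injector. Those features are present in both arms, carried by the active liquid in one and the placebo liquid in the other. A subject-level ISR rate by arm counts a reaction at either site, so it cannot separate a reaction to the auto-injector from a reaction to the pen.

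With no ISR test or between-arm contrast planned, readers will compare two percentages and their intervals by eye. Similar percentages are what one would see whether the liquid vehicle and device were benign or irritant. The risk is that similar rates are read as equal injection-site tolerability of the two products, on one of the two safety topics the protocol singles out.

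**Working it through.** **No plan figure to reproduce.** The documents give no expected ISR rate, margin or power for this trial. The HbA1c sample size reproduces (t-test power 0.9015 at 133 per arm) and is not affected. What follows illustrates how much cancels; the per-injector rates are assumptions.

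**Anchor.** Protocol 2.1 reports that "a low incidence (4.4%) of ADA was detected". Table 2 gives ISR rates of 41% in antibody-positive and 14% in antibody-negative subjects:

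0.044 × 0.41 + 0.956 × 0.14 = 0.018 + 0.134 = 0.152.

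This comes from Phase III studies of 32 weeks to 3 years, so it is not a 26-week rate. I use 0.15 for the active pen site.

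**Notation.** vP = risk at a placebo-pen site; vL = risk at a placebo-liquid site; E = vL − vP, the pure pH, volume and device excess; a = protein-related risk = 0.15 − vP.

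**Additive model, independent sites.**
- Liquid arm: 1 − (1 − vL − a)(1 − vP)
- Lyophilized arm: 1 − (1 − vP − a)(1 − vL)
- Difference: a × (vL − vP) = a × E

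With vP = 0.05, a = 0.10 and vL = 0.15, the liquid arm is 1 − 0.75 × 0.95 = 28.75% and the lyophilized arm is 1 − 0.85 × 0.85 = 27.75%, a difference of 1.0 point. With E = 0.10 and vP = 0, 0.05, 0.10, 0.15, the differences are 1.5, 1.0, 0.5 and 0.0 points. At least 85% of the excess cancels.

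**Multiplicative model, independent risks.** Both arms equal 1 − (1 − vL)(1 − vP)(1 − a), so the difference is exactly 0 whatever vL is. Example: vP = 5%, a = 5%, vL = 20% gives 1 − 0.95 × 0.95 × 0.80 = 27.8% in both arms. The active sites alone are 24.0% (1 − 0.95 × 0.80) and 9.75% (1 − 0.95 × 0.95), about 14 points apart.

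**Correlated sites.** If the same people tend to react at both sites, less cancels. Using a bivariate normal latent variable with correlation r, additive risks and E = 10 points, the by-arm difference in points is:

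| r | vP 3% | vP 5% | vP 10% | vP 15% |
|---|---|---|---|---|
| 0.3 | 2.2 | 1.8 | 0.8 | 0.0 |
| 0.5 | 3.1 | 2.5 | 1.2 | 0.0 |
| 0.7 | 4.5 | 3.6 | 1.7 | 0.0 |

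**Precision at 150 per arm.**
- One arm at 42/150 (28%): exact 95% CI 21.0% to 35.9%.
- Arm difference, 28.75% vs 27.75%: half-width 1.96 × √(0.2875 × 0.7125/150 + 0.2775 × 0.7225/150) = 10.2 points.

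Every residual in the table lies well inside that interval.

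**Active-injector sites instead.** 25% vs 15%: 10 ± 1.96 × √(0.25 × 0.75/150 + 0.15 × 0.85/150) = 10 ± 9.0 points, or 1.0 to 19.0.

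**What the by-arm display still detects.** A 10-point excess tied to the active protein in the liquid appears as 10 × (1 − vP), which is 8.5 to 10.0 points for vP from 15% to 0.

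**Weekly rates do not rescue it.** The auto-injector volume rises from 0.6 to 1.0 mL in both arms when the dose rises (Protocol 6.1 and 6.3). A before-and-after comparison therefore mixes volume with dose and time.

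**The case against.** The strongest reply is that the gap may not exist. Protocol 7.4.1.5 gives ISRs a dedicated eCRF page, and the injector is a natural field for it. Table 3.144 and Listing 25 could report it, and neither the shells nor the eCRF are in the documents. This stands as a limit: the point concerns what is specified, and it does not show that the injector went unrecorded. An open promise to summarize characteristics is still not a prespecified comparison.

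Second, the degree of cancellation depends on the model. At r = 0.9 with a 3% placebo-pen rate, 7.0 of the 10 points survive. That is correct, but it is an extreme combination, and 7.0 points is still within ±10. Table 2 also describes the ISR rate with placebo pens as clinically relevant, and a higher placebo-pen rate means more cancellation.

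Third, Table 2 does not confine its concern to the vehicle. An interaction of the protein with pH, volume or concentration, and antibody-linked reactions, would show by arm. This stands, so the display is insensitive to only part of the concern.

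Fourth, the by-arm rate is the blinded, randomized comparison, and the plan makes no equivalence claim for ISRs. This is a reason to keep it, but it does not remove the risk of misreading similar rates.

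Fifth, attribution to an injector is open to device and may be wrong for some reactions. The 1.0 to 19.0 interval assumes every reaction is attributed correctly.

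**Conclusion.** The concern holds. As specified, the ISR analysis is largely insensitive to reactions caused by the liquid's pH, volume or device, and similar arm rates would not show equal injection-site tolerability. For an assumed 10-point excess, the arms would differ by 0 under the multiplicative model, by 0 to 1.5 points under the additive model with independent sites, and by up to 4.5 points at a latent correlation of 0.7. A difference between arms is known only to about ±10 points.

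The cancellation itself follows from the double-dummy design with a matched placebo liquid. Its exact degree rests on three assumptions: the 15% active-site anchor, the unknown split between protein and vehicle effects, and the within-subject correlation. Protein- and antibody-related differences remain visible. The point should be addressed, but it touches neither the primary endpoint nor the sample size. Confidence is medium because the eCRF and table shells cannot be seen.

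**What to change.** Keep the by-arm tables. First establish whether the ISR eCRF page records the injector.

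If it does, add two descriptive displays to SAP 8.2.2 and Table 3.144:
- subjects with an ISR at the active-injector site, liquid vs lyophilized, with the risk difference and 95% CI;
- within each arm, a within-subject tabulation of auto-injector vs pen reactions, footnoted as not blinded to device.

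Report separately any reactions that cannot be assigned to one injector.

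If the injector was not captured, say in the study report that the by-group ISR comparison is largely insensitive to effects of the liquid's pH, volume or device.

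The cost is two tables or one sentence. No test is added, so the descriptive approach of Protocol 9.4.2 is unchanged. No new eCRF field is proposed: SAP 11.8.1 already holds the final region grouping, which was to be set after randomization, and SAP 11.1.2 cites deviation rules dated 21 June 2017, so it is late to change data capture. The price is some unattributable reactions and an attribution made knowing the device, though not which injector is active.
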